5 SCREENING AND CONSENT

5.1 Screening

Patients will be identified for both the feasibility study and RCT from newly diagnosed patients with stage IV (metastatic, inoperable) NSCLC (all histology subtypes) (see Appendix 7). Suitable patients will be identified during MDT meetings and will be approached at a subsequent clinic visit with their respiratory physician or oncologist, where the study and potential inclusion will be discussed.

Patients will be given a copy of the appropriate Patient Information Sheet (PIS) and a follow-up visit will be arranged to allow for patient questions and consent, should the patient so wish. Consent must be obtained within four weeks of diagnosis confirmation by the MDT, and ideally within two weeks. The feasibility study will address, confirm and inform the most appropriate time scales to be carried into the RCT.

The reason for screening failures should be captured on the Patient Screening/Enrolment Log which will be reviewed by the Trial Office in order to monitor uptake and identify issues with eligibility. Please note that for the feasibility study patients with clinical diagnosis only should also be included on the Log, so that the number of these patients can be quantified, these patients will not take part in the feasibility study. An Eligibility Checklist should be completed for each patient.

Page | 7 of 64 Version 1.0a, 8 Apr 2016

5.2 Informed Consent

It is the responsibility of the investigator to obtain written informed consent for each patient prior to performing any study or trial related procedure. Appropriate PIS (i.e. one for the feasibility study and one for the RCT) are provided to facilitate this process. Investigators must ensure that they adequately explain the aim, intervention, anticipated benefits and potential hazards of taking part in the study or trial (as appropriate) to the patient. The PIS will inform patients about the qualitative aspect of the research which includes an interview with a Qualitative Researcher from Sheffield.

The investigator should stress that the patient is completely free to refuse to take part or withdraw from the study or trial (as applicable) at any time. The patient should be given ample time (e.g. 24 hours) to read the appropriate PIS and to discuss their participation with others outside of the site research team. The patient must be given an opportunity to ask questions which should be answered to their satisfaction. The right of the patient to refuse to participate in the research without giving a reason must be respected.

If the patient expresses an interest in participating in the trial they will be asked to sign and date the latest version of the appropriate Patient Informed Consent Form. The investigator must then sign and date the form. A copy of the form will be given to the patient, a copy filed in the patient's medical records and the original placed in the Investigator Site File (ISF). Once the patient is entered into the trial the patient's registration number (feasibility study) or trial number (RCT) will be noted on their consent form, and the form filed in the ISF. In addition, if the patient has given explicit consent, a copy of their signed consent form must be sent in the post to the Trial Office for review. Patients agreeing to take part in the optional Qualitative Interviews will be asked to sign an additional consent form documenting this.

Once the patient has given consent the patient's primary carer will be informed about the trial, given the appropriate Carer's Information Sheet (i.e. for the feasibility study or RCT) and given time (e.g. 24 hours) to consider participating. The investigator should stress that the carer is completely free to refuse to take part or withdraw from the study or trial (as applicable) at any time. If they agree to participate they will be asked to sign and date the appropriate Carer's Informed Consent Form. This form should be countersigned by the investigator. The Carer's Informed Consent Form will be copied and filed as detailed above for the Patient Informed Consent Form, with a copy being sent to the Trial Office for in-house review if the carer has consented to this. Carers agreeing to take part in the optional Qualitative Interviews will be asked to sign an additional consent form documenting this.

Details of all of the informed consent discussions should be recorded in the patient's medical records, this should include date of, and information regarding, the initial discussion, the date consent was given, with the name of the trial and the version number of the Patient and Carer Information Sheets and Informed Consent Forms. Throughout the trial participants should have the opportunity to ask questions about the trial and any new information that may be relevant to their continued participation should be shared with them in a timely manner. On occasion it may be necessary to re-consent the participant in which case the process above should be followed and the patient's and or carer's right to withdraw from the trial respected.

Electronic copies of the Patient and Carer Information Sheets and Informed Consent Forms are available from the Trial Office and should be printed or photocopied onto the headed paper of the local institution.

6 TRIAL ENTRY

For both the feasibility study and the RCT written informed consent must be obtained prior to a patient's entry into the trial and recorded on the appropriate Informed Consent Form. An Eligibility Checklist should also be completed prior to registration or randomisation, as appropriate.

The name of the investigator directly responsible for the patient's care will be requested at registration/randomisation. Investigators must be registered with the Trial Office before they are permitted to register patients into the trial (see Section 17.1).

6.1 Feasibility Study - Registration

To register a patient into the trial complete the Registration Form and call Cancer Research UK Clinical Trials Unit (CRCTU) at the University of Birmingham on the number below:

2 [name]

9.00 am till 5.00 pm Monday to Friday

The CRCTU Randomisation Office will be closed on Bank Holidays and University of Birmingham closed days.

Sites will be informed of forthcoming closures in advance.

The following information should be provided:

- Name of site and investigator
- Patient's initials
- Date of birth
- Confirmation of eligibility
- Date of patient consent
- Whether the patient has consented to the optional aspects of the study. If the patient has consented to the Qualitative Interviews their full name and telephone number will be collected
- Details of carer consent including their initial's, whether they have consented to the qualitative interviews. If the patient has consented to the Qualitative Interviews their full name and telephone number will be collected)

The CRCTU will assign each feasibility study patient with a unique registration number that must be noted on the Registration Form, Informed Consent Form, as well as all subsequent Case Report Forms (CRFs). The completed Registration Form, Eligibility Checklist and a copy of the Informed Consent Form should to be sent to the Trial Office.

With the patient's prior consent their General Practitioner (GP) should also be informed that they are taking part in the trial. A feasibility study GP Letter is provided electronically for this purpose.

6.2 Randomised Controlled Trial - Randomisation

To randomise a patient into the RCT complete a Randomisation Form and call the CRCTU using the number below.

2 [name]

9.00 am till 5.00 pm Monday to Friday

The CRCTU Randomisation Office will be closed on Bank Holidays and University of Birmingham closed days.

Sites will be informed of forthcoming closures in advance.

The following information should be provided:

- Name of site and investigator
- Patient's initials
- · Date of birth
- · Confirmation of eligibility
- Date of patient consent
- Whether the patient has consented to the optional aspects of the study. If the patient has consented to the Qualitative Interviews their full name and telephone number will be collected)
- Details of carer consent including their initial's, whether they have consented to the qualitative interviews. If the patient has consented to the Qualitative Interviews their full name and telephone number will be collected)

Patients will be randomised using a computerised minimisation technique. Stratification variables include:

- Site
- Age (<50 years, ≥50 year)
- The presence or absence of brain metastases
- mGPS (scores 0, 1 or 2)

Patients will be randomised one-to-one to the following arms:

- Arm A: Standard Care
- · Arm B: Early referral to SPC

Patients allocated to Arm B will undergo a second randomisation (1:1) to:

- Arm B1: Sites Standard SPC
- Arm B2: Sites Standard SPC + SPARC

Patients will be issued with a unique Trial Number which should be used on all correspondence with the Trial Office.

The completed Randomisation Form, Eligibility Checklist and a copy of the Informed Consent Form should be sent to the Trial Office.

With the patient's prior consent their GP should also be informed that they are taking part in the trial. A RCT GP Letter is provided electronically for this purpose.

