4.1 Inclusion Criteria

- Any adult (≥18 years) patient with newly diagnosed stage IV NSCLC, with histologically confirmed diagnosis
- ECOG performance score 0-3 (see Appendix 6)

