19.1.4 Planned Sub-group Analyses

Where appropriate outcome measures will be analysed by mGPS and ECOG performance score, accordingly.

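### Section 6.2 does not minimise on ECOG performance status, although it is known before randomisation and would cost one extra field to balance

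*Protocol*

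**What the plan says.** Section 6.2 of the protocol introduces the allocation method with "Patients will be randomised using a computerised minimisation technique. Stratification variables include", followed by four items: site, "Age (<50 years, ≥50 year", "The presence or absence of brain metastases" and "mGPS (scores 0, 1 or 2". The main allocation is 1:1 between standard care and early referral. ECOG is not on the list.

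Other sections bear on whether it could be:

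- Section 4.1 admits "ECOG performance score 0-3 (see Appendix 6". By Appendix 6 that runs from fully active patients to those who spend most of the waking day in bed or a chair.
- Section 6 says: "An Eligibility Checklist should also be completed prior to registration or randomisation, as appropriate". ECOG is therefore known at the randomisation call, and section 7.2.2.1 takes the eligibility value as the baseline value.
- Section 19.1.4, on the feasibility stage, says: "Where appropriate outcome measures will be analysed by mGPS and ECOG performance score, accordingly".
- Section 2.2.2 names mGPS and the co-morbidity index as variables to help explain variation in outcomes. It does not name ECOG.
- Section 19.2.2.1 outlines a t-test for each co-primary outcome and leaves full detail to the SAP.

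**The concern.** Of the two variables that section 19.1.4 uses to break down feasibility outcomes, only mGPS is carried into the minimisation. ECOG plausibly bears on all that the primary comparisons depend on: global health status, survival within the quality-adjusted survival measure, and whether a patient is well enough at three months to enter the GHSS analysis. Section 1.1 itself describes this population as having poor performance status.

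Minimisation factors are fixed in the protocol and cannot be added once recruitment is complete. If ECOG is neither balanced by design nor adjusted for, a chance difference between arms would feed straight into an unadjusted comparison of means. It would also invite doubt about an unblinded trial with patient-reported outcomes.

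**Working it through.** **1. The plan's own figures.** Section 19.2.5 gives a GHSS difference of 7, SD 23, two-sided 5% and 35% loss. For 80% power the normal formula gives 2 × (1.960 + 0.842)² × (23/7)² = 169.5, so 170 per arm and 340 in total. The exact t-test gives 342, as stated, and 456 for 90% power. Dividing 342 by 0.65 gives 526 against the stated 525. For quality-adjusted survival (0.5 month, SD 2) the exact t-test gives the stated 506 and 676. Nothing below changes a sample size.

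**2. Assumptions.** The protocol gives neither the share of patients at ECOG 2-3 nor the GHSS gap between ECOG groups. I take a share q of 20-40% and a gap of 10-20 points. Any indirect balance through mGPS is ignored, so the imbalance figures are upper estimates.

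**3. Imbalance among all 525.** Under 1:1 allocation that takes no account of ECOG, the SD of the arm difference in the share at ECOG 2-3 is √(4q(1−q)/N).

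- q = 0.20: √(0.64/525) = 3.49 points; 5/3.49 = 1.43; two-sided probability 15%.
- q = 0.40: √(0.96/525) = 4.28 points; 5/4.28 = 1.17; two-sided probability 24%.

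**4. Imbalance among GHSS completers.** 525 × 0.65 = 341.

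- q = 0.20: SD 4.33 points; chance of 5 points or more 25%.
- q = 0.40: SD 5.31 points; chance of 5 points or more 35%.

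Balancing at entry does not remove all of this. With perfect balance at 525, a random 65% subset still keeps 1 − 0.65 = 35% of the variance, so each SD is multiplied by √0.35 = 0.59.

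- q = 0.20: 4.33 × 0.59 = 2.56 points; probability 5%.
- q = 0.40: 5.31 × 0.59 = 3.14 points; probability 11%.

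If death or dropout differed by arm, more imbalance would remain.

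**5. Effect on the GHSS difference.** With q = 0.30 and 342 analysed, the SD is √(0.84/342) = 4.96 points and the 95% range is ±9.7 points. Multiplied by a gap of 10 or 20, the arm difference shifts by up to ±0.97 or ±1.94 points, which is 14% or 28% of the 7-point target. An imbalance of exactly 5 points shifts it by 0.5 to 1.0 point.

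**6. What adjustment would add.** With q = 0.30, a gap of 10 or 20 accounts for 0.21 × 100/529 = 4% or 0.21 × 400/529 = 16% of the outcome variance. Power is Φ(7/(23 × √(1−R²) × √(2/171)) − 1.96). That is 80% unadjusted, 82% at R² = 0.04 and 87% at R² = 0.16.

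**The case against.** The strongest reply is that prognosis is already balanced. mGPS enters at three levels, is built from two laboratory values, and is described in section 2.2.2 as primarily a prognostic and stratification measure. Preferring it to a rated scale is a reasonable choice. This stands in part: ECOG is not left wholly to chance, and the figures above overstate the imbalance by an unknown amount. But ECOG and mGPS are different measures, and section 19.1.4 lists both.

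A second reply is that the effect is small and does not threaten validity. That stands. Chance imbalance neither biases a randomised comparison nor inflates the type I error.

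A third reply is that the design was still open. The factor list is introduced as what the variables include, the feasibility stage is meant to inform the RCT design, section 3.1.1 foresees protocol amendments, and the SAP may adjust for ECOG. This makes the change easy. It does not put ECOG on the list, and the SAP cannot supply a minimisation factor.

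Two stronger readings are tempting. One is that the cut at 50 puts nearly every patient in one age group and so wastes a factor. The protocol gives no age distribution, only a lower limit of 18. Section 10 uses the same cut for qualitative sampling and seeks at least three patients or carers per age-by-gender subgroup at each of four sites, so its authors expected some people under 50. If 1-20% of patients were under 50 (assumed), the smaller stratum would hold about 5 to 105 of 525, and the documents do not say where in that range it falls. The other is that section 19.1.4 calls ECOG a key variable. It does not: it only breaks down descriptive feasibility outcomes by it, where appropriate.

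**Conclusion.** The point holds as a design weakness of modest size; it is not an error or contradiction. A baseline variable that is already collected, and that the protocol uses alongside mGPS, is missing from the minimisation and is not among the explanatory variables named for analysis.

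Under the assumed ECOG mix, balancing would remove a 15-24% chance of an imbalance of 5 points or more at entry. Among GHSS completers it would cut that chance from 25-35% to about 5-11%. The likely consequence for the GHSS result is at most about 1-2 points against 7. All these sizes rest on assumed ECOG shares and GHSS gaps. The absence of ECOG from the list does not.

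No conclusion on the age cut follows from the documents, and they give no ground for removing age to make room for ECOG.

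**What to change.** Before the RCT opens, amend section 6.2 in two ways:

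- Add ECOG, for example in two levels (0-1 v 2-3), to the minimisation variables, using the value already recorded for eligibility, and keep site, age, brain metastases and mGPS.
- Word the list as complete, so that the factors are fixed.

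In section 19.2.2.1, or in the SAP, include ECOG as a pre-specified covariate in both primary analyses. Adjustment also deals with the imbalance that can re-emerge among GHSS completers. When the feasibility data are in, tabulate age and ECOG, then either give the reason for the cut at 50 or revise it.

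The cost is one more field in the randomisation call and a change to the randomisation specification. A fifth factor may slightly loosen balance on the other four. No new assessment is needed and no sample size changes.

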7 ASSESSMENTS AND DELIVERY OF INTERVENTION

SPC will be delivered variably according to local service configuration. In some sites the service will be run within the NHS; in others it will be supplied from a local independent charitable hospice service. In essence, all SPC services are supplied by a combination of specialists trained in palliative medicine and nursing, and other clinical and allied health professionals who may have varying degrees of specialisation. Both stages of the study will describe and characterise which elements of these are applied, in what order and to what degree.

Sites in which all patients are referred early, i.e. within two to four weeks, to SPC will not be eligible to participate in this trial. In addition, in order to be able to participate as a site in the RCT trial, the SPC input should be offered by a palliative medicine doctor and nurse.

Health technologies which are used during the process of cancer care and symptom management for trial patients will also captured in both stages of the trial. These include:

- · Radiotherapy including date of last dose in relation to time of death
- Cytotoxic chemotherapy including date of last dose in relation to time of death
- Targeted biological therapy including date of last dose in relation to time of death
- Other interventional health technologies (see Appendix 1 for details)
- Use of interventions around the end of life (see Appendix 1 for details)

7.1 Feasibility Study

Patients in the feasibility study will not receive any intervention and should be treated in accordance with the sites standard care pathway. The SPARC HNA tool will be piloted.

7.1.1 Feasibility Study Assessment Schedule

The patient visit schedule is summarised in Table 1.

Table 1: Patient Visit Schedule - Feasibility

Assessment	Screening/ Baseline	Follow-up Period	After Death
		Monthly, or to coincide with treatment schedule for 6 months	
Eligibility check	X		
ECOG Performance Status	X	X	
Patient's Informed Consent	X		
Carer's Informed Consent (once patient has consented)	X		
Patient Registration	X		
Demography, medical history	X		
Concomitant medication	X	X	
Modified Glasgow Prognosis Score (mGPS)	X	X*	
Scottish lung cancer co-morbidity index	X		
Patient Questionnaire Booklet (time-point specific)	X	X	
Sheffield Profile for Assessment and Referral for Care (SPARC) ALL PATIENTS	X	X	
Patient Acceptability of Randomisation Questionnaire	X		
Patient diary collected		X	
Montreal Cognitive Assessment scale (MoCA) (consenting participants only)	X	X*	
Carer Questionnaire Booklet	X	X	
Qualitative Interviews (consenting participants only)		X [‡]	
Patient Feedback Questionnaire		χ [†]	
Recording of resource use		X	
Treatment details and measurement of response (as per local practice)		X	
Relapse/Progression		X	
Notification of death, location of death			Х
Clinical Records Review: Interventions and Specialists seen during month leading up to death			Х
CODE™ (consenting participating carers only; 2-3 months post-bereavement)			Х

Notes

Page | 12 of 64 Version 1.0a, 8 Apr 2016

^{*} mGPS & MoCA will be measured at 3 and 6 months during follow-up (see Section 7.3)

[‡] Performed between 6 weeks and 3 months follow-up [†] Completed at the 3 month follow-up only

7.1.1.1 Baseline Assessments

Baseline assessments must be within two to four weeks of the patient being diagnosed and as soon as possible after feasibility study entry. The following assessments should be performed and will be captured on the CRF:

- mGPS (see Appendix 3 and Section 7.3)
- Demographics
- Medical history
- Scottish Lung Cancer Co-morbidity Index Score (see Appendix 5, for list of co-morbidities and scores)
- Current concomitant medications
- SPARC (see Appendix 2)
- ECOG (as per eligibility assessment; see Section 4.1 and Appendix 6)
- MoCA (see Appendix 4) only for those patients who consent to this optional measure of cognitive function

The patient should be asked to complete the following during the clinic appointment:

- Acceptability of Randomisation Questionnaire
- Baseline Patient Questionnaire Booklet

The carer should also be given the Carer Questionnaire Booklet if they have agreed to participate in the study.

Prior to completing the questionnaire a member of the site research team should discuss the questionnaires with the patient, and if applicable the carer, and answer any questions they may have. Once the questionnaires have been completed by the patient/carer the site research team should check to make sure that all of the questions have been completed and that, in particular, the date the questionnaires are completed and the patient's registration number has been accurately recorded.

The patient should also be given the Patient Diary (this will have sufficient diary sheets to last for six months). Completion of the diary should be explained to them and they should be asked to return completed sheets at their next appointment.

7.1.1.2 Follow-up Assessments

The patient should be followed-up at least once per month for six months. Patients being treated every third week (for example those receiving chemotherapy) will be seen every three weeks while on treatment. The patient's visits should be organised to correspond with their treatment visits where possible.

The following should be assessed at each visit (be that three weekly of four weekly):

- Disease status
- ECOG status (see Appendix 6)
- Concomitant medication

The patient should be asked to complete the following during the clinic appointment:

- Appropriate Follow-up Patient Questionnaire Booklet
- SPARC (see Appendix 2)

In addition to the above, at the **three and six month assessments**, the following must also be assessed:

- mGPS (see Appendix 3 and Section 7.3)
- MoCA (see Appendix 4) only for those patients who consent to this optional measure of cognitive function

The patient should be asked to complete the Patient Feedback Questionnaire at their 3 month followup assessment

The carer should be asked to complete the Carer Questionnaire Booklet. If the trial registered carer is not accompanying the patient, please send the carer questionnaire booklet home with patient so that the carer may complete and return it to the site research team at the next follow-up clinic visit.

Completed questionnaire booklets and forms should be returned to the Trial Office with the patient's completed diary sheets.

Please note: The patient may require a new Patient Diary after their six month assessment visit.

A larger format version of the diary is available (A4, larger font size) for patients who require large print.

The following information will be collected on the CRF at all follow-up visits:

- Disease status
- ECOG status (see Appendix 6)
- Concomitant medication
- Treatment details
- Response to treatment (determined as per local practice)
- Hospital admissions, including duration and reason for admission
- Details of relapse/progression
- Details of patient referral to the SPC team
- Resource use (see Appendix 1 for list of medical interventions)

